## Abstract

Title	Hyperpolarized  C pyruvate metabolic MRI for treatment response assessment in pancreatic ductal adenocarcinoma
Study Description	This is a pilot prospective study to investigate the utility of HP 13C pyruvate MRI for assessing tumor metabolism and monitoring early treatment response in patients with locally advanced or metastatic PDA.
Phase of Study	Pilot
Investigational Product	HP  C pyruvate injection
Study Population	Patients with locally advanced or metastatic pancreatic ductal adenocarcinoma (PDA) will be enrolled in parallel in one of two cohorts:
	Cohort A (N=20): Patients who are already on therapy will undergo hyperpolarized (HP) $^{13}$ C pyruvate MRI at a single time-point.
	Cohort B (N=20): Patients will undergo HP $^{13}$ C pyruvate MRI at baseline prior to the initiation of a new line of therapy (standard-of-care first- or second-line systemic therapies, radiotherapy, or therapies as part of a clinical trial), and again at 4 weeks (+/- 2 weeks) following treatment initiation.
Primary Objective	Cohort A: To determine the signal-to-noise ratio of 13C pyruvate metabolism measures (peak 13C lactate/pyruvate ratio, 13C lactate/pyruvate area-under-the- curve (AUC) ratio, and apparent rate constant for pyruvate-to-lactate conversion, kPL) in the target tumor (primary tumor and/or abdominal metastases).
	Cohort B: To determine the percent changes in the target tumor (primary tumor and/or abdominal metastases) 13C pyruvate metabolism measures (peak 13C lactate/pyruvate ratio, 13C lactate/pyruvate AUC ratio, and kPL) between pre-treatment scan and scan obtained at 4-week (+/- 2 weeks) following treatment initiation.
Secondary Objectives	Cohort A and B: To determine the repeatability of 13C pyruvate metabolism measures in the target tumor (primary tumor and/or abdominal metastasis) in patients with same-day repeated dose.
	Cohort B: To determine whether the baseline or the changes in the target tumor (primary tumor and/or abdominal metastases) 13C pyruvate metabolism measures at 4 weeks (+/-2 weeks) following treatment initiation are associated with the best objective response as defined by RECIST criteria on subsequent clinical CT scans.
Exploratory Objective	Cohort A and B: To explore 13C pyruvate metabolism between the primary tumor and abdominal metastases (when present) both at baseline and following treatment.

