#### **1.3** Rationale for use of HP C Pyruvate in patients with pancreatic cancer

Need for rapid response monitoring in PDA: Pancreatic ductal adenocarcinoma (PDA) is the 3rd leading cause of cancer related death in the US and is anticipated to become the 2nd by 2030(7). The majority of PDA patients (> 75%) present with locally advanced or metastatic disease for which systemic chemotherapy is the only life-prolonging treatment (8). The length of time these patients spend on effective therapy is the most important factor in their survival. Therefore, there is an urgent need for biomarkers to accurately assess treatment response, and to do so early so that patients can be spared the significant toxicities of ongoing ineffective treatment and can instead be offered alternative treatment (i.e. combination chemotherapy of a differing backbone from that administered in the first line) with a better chance of efficacy. Additionally, we need alternative endpoints for clinical trials other than overall survival, which is often complex in PDA and is often a function of treatment efficacy coupled with performance status and other factors. *Given the deadliness of this disease, we need to rapidly determine response in order to inform decision of whether to continue an effective treatment or discontinue an ineffective one (9).* 

Limitations of current response assessment tools in PDA: Objective treatment response in PDA is commonly assessed by measuring changes in tumor size at anatomic imaging according to RECIST (Response Evaluation Criteria in Solid Tumors) criteria several months into treatment. However, a change in tumor size is a relatively late endpoint in PDA. In addition, monitoring response to therapy in the primary tumor is particularly challenging because of the extensive

[figure not shown]
Version date: 07/29/2022

desmoplasia and inflammation associated with the tumor and the difficulty in defining tumor margin (10). As a result, many patients' functional status declines while we wait to determine whether or not the treatment is working at imaging read-out points (typically 8-12 weeks apart following treatment initiation). *Many of these patients progress after months of ineffective therapy and are no longer suitable for second line therapy nor eligible for second line trials, resulting in worse survival.* 

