## 2.3 Secondary Objectives and Endpoints

Secondary Objective	Endpoint(s)	Time Frame

 
To determine the repeatability of C pyruvate metabolism measures in the target tumor (primary tumor and/or abdominal metastasis) in patients with same-day repeated dose in Cohort A and B.
 
	
 
repeatability of C pyruvate metabolism measures in the target tumor
 
	From study initiation to enrollment of last subject
2. To determine whether the baseline or the changes in the target tumor (primary tumor and/or abdominal metastases)  C pyruvate metabolism at 4 weeks following treatment initiation are associated with the best objective response as defined by RECIST criteria on subsequent clinical CT scans in Cohort B.	
 
The association between the baseline target tumor pyruvate metabolism and tumor best objective response as defined according to RECIST criteria on subsequent standard-of-care CT.
 
The association between the changes in the target tumor pyruvate metabolism post treatment initiation and tumor best objective response as defined according to RECIST criteria on subsequent standard-of-care CT.
 
	From study initiation to up to 18 months following enrollment of last subject

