#### 3.3 Replacement Policy

Patients may be replaced for the following reasons:

- Inability to tolerate/complete imaging scan (with no administration of HP C pyruvate)
- Failure of the HP C pyruvate to pass testing, preventing its administration
- Patients who do not subsequently undergo treatment following the baseline HP C pyruvate MRI

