#### 3.4.1 Inclusion Criteria

Subjects may be included in the study if they meet all of the following criteria:

- 1. Subjects must be 18 years or older.
- 2. Locally advanced or metastatic pancreatic ductal adenocarcinoma, with at least one target lesion in the abdomen measuring  $\geq$  1cm.

The subject is able and willing to comply with study procedures and provide signed and dated informed consent.

Eastern Cooperative Oncology Group (ECOG) Performance Status of 0 or 1.

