## 8.1.2 Accrual Estimates

It is estimated that 1-2 subject will be enrolled per month, and approximately 36 months will be required to complete accrual and data acquisition to the study. In the case of subjects being unevaluable for analysis of primary endpoint, additional subjects may be enrolled to reach the required total number of evaluable subjects.

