#### 8.3 Analysis Plans

Data from all subjects dosed in the study will be included in all listings, plots, summary tables, and statistical analyses when appropriate. Missing values will not be substituted by estimated values, but treated as missing in the statistical evaluation.

In this pilot study, we will focus on the primary PDA HP C pyruvate metabolism (if present) because accurate assessment of treatment response in the primary PDA is particularly challenging on conventional imaging given its infiltrative nature(10). If the primary tumor has been resected, we will then focus our analysis on the largest abdominal metastasis that is amenable to HP MRI.

We will not explicitly adjust for multiple comparisons in analyzing the data in this pilot study.

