### 8.3.3 Secondary Analysis

Cohort A and B: Repeatability of C pyruvate metabolism measures in the target tumor (primary tumor and/or abdominal metastasis) in patients with same-day repeated dose.

Cohort B: The association between the baseline or changes in the target tumor pyruvate metabolism at 4 weeks post treatment initiation and tumor best objective response as defined according to RECIST criteria on subsequent standard-of-care CT.

Secondary endpoint analysis: For Cohort A and B, intraclass correlation coefficient (ICC) will be used to estimate the intra-subject agreement to assess repeatability of tumor HP C pyruvate metabolism in patients with same-day repeated dose.

ICC will be used to estimate agreement, and obtained from a one-way analysis of variance model based on 2 measurements per subject. The result will be presented with a 95% confidence interval. If 20 (out of 40) subjects had repeated dose of the hyperpolarized 13C pyruvate, we will have 90% power to show an ICC of at least 0.6.

For Cohort B, tumor best objective response will be defined using RECIST 1.1 on subsequent clinical CT scans. For the purpose of response assessment in this pilot study, we will group patients either as having disease control when the best response is complete response (CR), partial response (PR), or stable disease (SD) on subsequent clinical CT scans, or having disease progression when the best response is progressive disease (PD) on subsequent CT scans. Based on prior published studies (37, 38) in PDA patients who receive first- or second-line therapies (i.e. FOLFIRINOX, gemcitabine plus nab-paclitaxel, or gemcitabine monotherapy), we estimate an average 50% disease control rate for this group of patients. We will compare the baseline or changes in the target tumor C pyruvate metabolism at 4 week (+/-2 weeks) after treatment initiation between the disease control group and disease progression group (as defined by RECIST on subsequent clinical CT scans) using the Mann-Whitney tests.

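### Cohort B response is assigned only from a later CT, so treated patients who die of the cancer or progress clinically without one drop out of the response comparison

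*Combined protocol and SAP*

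**What the plan says.** The Abstract and section 2.3 ask whether the baseline measures, or their change at 4 weeks, are "associated with the best objective response as defined by RECIST criteria on subsequent clinical CT scans". Section 8.3.3 then forms two groups. Disease control means a best response of CR, PR or SD on later clinical CT. The other group is defined as "having disease progression when the best response is progressive disease (PD) on subsequent CT scans". Baseline values and changes are compared between the groups by Mann-Whitney tests, with an expected disease control rate of 50%.

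Section 8.3 sets the missing-data rule: "Missing values will not be substituted by estimated values, but treated as missing in the statistical evaluation". The time frame for this objective in section 2.3 is "From study initiation to up to 18 months following enrollment of last subject". The calendar in section 6.1 takes disease assessment from standard-of-care CT at 2-3 month intervals and has no row for survival or clinical progression.

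**The concern.** Neither group has a place for a treated patient with no CT after treatment start. If that patient died of the cancer or was recorded as progressing clinically, the treatment is known to have failed, yet under the missing-data rule the patient is left out.

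The case is foreseeable. Section 1.3 says that many patients' "functional status declines while we wait to determine whether or not the treatment is working at imaging read-out points", with read-outs typically 8-12 weeks apart.

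This is the only planned analysis that links the imaging measures to response, and so the only one that bears directly on the hypothesis in section 2.1. Because the excluded patients are known failures, the loss comes from one group of about ten. If loss is unrelated to metabolism, it costs power. If it is related to metabolic change, it also distorts the estimated separation.

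**Working it through.** **Does another section cover this patient?**

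- Section 3.3 (replacement) covers a scan not completed with no dose given, product that fails testing, and "Patients who do not subsequently undergo treatment following the baseline HP" 13C pyruvate MRI. A treated patient with both scans fits none of these.
- Section 8.1.2 provides that "In the case of subjects being unevaluable for analysis of primary endpoint, additional subjects may be enrolled". The primary endpoint needs the two scans, not a CT, so this patient is evaluable there and triggers no extra enrolment.
- Section 8.3.1 (analysis population) describes demographic summaries and has no evaluability rule for response.
- Section 8.3 says data from all dosed subjects are used where appropriate, but this does not assign a group.

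The gap therefore stands. It is limited to patients with no CT at all, since any later or unscheduled CT within the time frame still classifies a patient. In the change comparison it is limited further to patients who had the 4-week scan, because the others are lost for lack of a second scan.

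**Inputs.** From the documents: Cohort B n = 20 and 50% disease control, hence 20 × 0.5 = 10 v 10. Assumed, because the documents give nothing: two-sided alpha 0.05, normal data with unit SD, true separation 1.3 SD, and 1 to 4 of the 10 progressors lost. The plan states no power for this test, so there is no figure to reproduce.

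**Chance of at least one patient without a CT among 20** at an assumed rate q, 1 − (1 − q)^20:
- q = 5%: 1 − 0.95^20 = 64%
- q = 10%: 1 − 0.90^20 = 88%
- q = 20%: 1 − 0.80^20 = 99%

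**Power and separation for the change comparison.** Exact Mann-Whitney test, 40,000 simulated trials per scenario. Loss is ranked on z = ρ × change + √(1 − ρ²) × noise, and the L progressors with the highest z are removed. Positive ρ means that the most progressor-like patients tend to be lost. Full-data power is 74%.

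| Progressors lost (L) | Groups | ρ = 0: power; separation | ρ = +0.3: power; separation | ρ = −0.3: power; separation |
|---|---|---|---|---|
| 1 | 10 v 9 | 72%; 1.30 SD | 69%; 1.25 SD | 75%; 1.35 SD |
| 2 | 10 v 8 | 68%; 1.30 SD | 62%; 1.20 SD | 75%; 1.40 SD |
| 3 | 10 v 7 | 64%; 1.30 SD | 56%; 1.17 SD | 74%; 1.44 SD |
| 4 | 10 v 6 | 59%; 1.30 SD | 48%; 1.12 SD | 71%; 1.48 SD |

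Counting all of them correctly as progression restores 74% and 1.30 SD in every cell. With 3 lost at random, power falls from 51% to 43% at a separation of 1.0 SD, and from 85% to 77% at 1.5 SD. A repeat of the simulation agreed within about one percentage point on power and 0.01 SD on separation.

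The apparent disease control rate also rises, as 10/(20 − L): 53%, 56%, 59% and 63% for L = 1 to 4, against a true 50%.

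**Cost of misattribution.** Let *a* true progressors and *b* control-like patients lack a CT, with loss unrelated to metabolism. The current rule compares (10 − a) v (10 − b). Correct attribution compares 10 v (10 − b). Counting everyone without a CT as progression compares (10 + b) v (10 − b).

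| a, b | Current rule | Correct attribution | All counted as progression |
|---|---|---|---|
| 1, 1 | 67% | 72% | 65% |
| 2, 1 | 67% | 72% | 65% |
| 3, 1 | 61% | 72% | 65% |
| 2, 2 | 65% | 68% | 54% |

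One control-like patient wrongly counted also pulls the separation to 1.30 × 10/11 = 1.18 SD.

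**The case against.** The strongest reply is that this is a choice of endpoint. The outcome is an imaging response, a patient without an image is not evaluable for it, and adding death or clinical progression makes it a composite. The rule can be carried out as written. That is fair. But the plan reduces response to control versus progression, and for that contrast the excluded patient's status is known. A stated choice between the two readings is better than an exclusion that follows by default.

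The number affected may be small or zero, and this stands. Section 1.3 describes pancreatic cancer patients in general and does not say that they never reach a CT. Entry requires an ECOG "Performance Status of 0 or 1", the change comparison requires attendance at the 4-week scan, and follow-up is long.

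Every input to the magnitude except the 10 v 10 split is assumed, and this stands too. With one patient lost at random, power moves only from 74% to 72%. At ρ = −0.3 there is almost no power cost up to three lost; there the harm is an inflated separation.

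Reclassification can also do harm: one wrong attribution costs more than one or two correct ones recover. The apparent break-even at about three partly reflects the discreteness of the exact test and should not be read as a threshold. This argues for a restricted rule with a CT-only sensitivity analysis, not for leaving the gap.

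Finally, section 8.3.3 cites RECIST 1.1, whose text is not in the documents. The point rests only on the plan's own wording, which confines classification to CT findings.

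**Conclusion.** The concern holds, as a minor point. The textual gap is certain: as written, the plan excludes from its only imaging-response comparison treated patients whose failure is known but who have no later CT, and no other section recovers them. How often this happens, and in which direction any bias runs, cannot be determined from the documents.

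Under the stated assumptions, losing one to four of ten progressors at random lowers power by about 2 to 15 percentage points (74% to 72% through 59%). Loss modestly related to metabolic change would move the separation to between 1.12 and 1.48 SD, against a true 1.30 SD. The primary analyses are unaffected.

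**What to change.** Amend section 8.3.3, before response data are analysed, along these lines:

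*For the disease-control comparison, a patient with no evaluable CT after treatment start whose death is attributed to the cancer, or who has clinical progression recorded by the treating physician, is counted as disease progression. Deaths of unknown or unrelated cause, and other patients without a CT, are not evaluable.*

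Such patients enter the baseline comparison, and enter the change comparison only if the 4-week scan was done. Report the number without a CT by reason, and repeat both comparisons with CT-defined response only.

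The cost is a short amendment, signed and approved by the PRC and CHR under section 9.4, plus chart abstraction. Section 6.1 schedules no survival or clinical-progression assessment, so status and cause of death would come from the medical record, already the source document under section 9.6. The downside is that a few outcomes are classified without a CT measurement and some may be wrong. Leaving unknown causes not evaluable limits that risk, and the CT-only analysis shows whether it matters.

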## 8.3.4 Exploratory Analysis

The correlation in HP C pyruvate metabolism between the primary tumor and abdominal metastases (when present) at baseline and following treatment.

Exploratory endpoint analysis: Pearson correlation tests will be used to compare the HP C pyruvate metabolism between the primary tumor and abdominal metastasis when present.

#### 9 Study Management

#### 9.1 **Pre-study Documentation**

This study will be conducted in accordance with the ethical principles that have their origin in the Declaration of Helsinki as stated in 21 CFR §312.120(c)(4); consistent with GCP and all applicable regulatory requirements.

Before initiating this study, the Investigator will have written and dated approval from the Institutional Review Board for the protocol, written informed consent form, subject recruitment

materials, and any other written information to be provided to subjects before any protocol related procedures are performed on any subjects.

The clinical investigation will not begin until either FDA has determined that the study under the Investigational Drug Application (IND) is allowed to proceed or the Investigator has received a letter from FDA stating that the study is exempt from IND requirements.

The Investigator must comply with the applicable regulations in Title 21 of the Code of Federal Regulations (21 CFR §50, §54, and §312), GCP/ICH guidelines, and all applicable regulatory requirements. The IRB must comply with the regulations in 21 CFR §56 and applicable regulatory regulatory requirements.

#### 9.2 Institutional Review Board Approval

The protocol, the proposed informed consent form, and all forms of participant information related to the study (e.g. advertisements used to recruit participants) will be reviewed and approved by the UCSF CHR (UCSF Institutional Review Board). Prior to obtaining CHR approval, the protocol must be approved by the Helen Diller Family Comprehensive Cancer Center Site Committee and by the Protocol Review Committee (PRC). The initial protocol and all protocol amendments must be approved by the IRB prior to implementation.

#### 9.3 Informed Consent

All participants must be provided a consent form describing the study with sufficient information for each participant to make an informed decision regarding their participation. Participants must sign the CHR-approved informed consent form prior to participation in any study specific procedure. The participant must receive a copy of the signed and dated consent document. The original signed copy of the consent document must be retained in the medical record or research file.

#### 9.4 Changes in the Protocol

Once the protocol has been approved by the UCSF CHR, any changes to the protocol must be documented in the form of an amendment. The amendment must be signed by the Investigator and approved by PRC and the CHR prior to implementation.

If it becomes necessary to alter the protocol to eliminate an immediate hazard to patients, an amendment may be implemented prior to CHR approval. In this circumstance, however, the Investigator must then notify the CHR in writing within five (5) working days after implementation. The Study Chair and the UCSF study team will be responsible for updating any participating sites.

#### 9.5 Handling and Documentation of Clinical Supplies

The Principal Investigator will maintain complete records showing the receipt, dispensation, return, or other disposition of all investigational drugs. The date, quantity and batch or code number of the drug, and the identification of patients to whom IMP has been dispensed by patient number and initials will be included. The sponsor-investigator will maintain written records of any disposition of the IMP.

The Principal Investigator shall not make the investigational drug available to any individuals other than to qualified study patients. Furthermore, the Principal Investigator will not allow the investigational drug to be used in any manner other than that specified in this protocol.

## 9.6 Case Report Forms (CRFs)

The Principal Investigator and/or his/her designee will prepare and maintain adequate and accurate participant case histories with observations and data pertinent to the study. Study specific Case Report Forms (CRFs) will document safety and treatment outcomes for safety monitoring and data analysis. The Clinical Research Coordinator (CRC) will complete the CRFs as soon as possible upon completion of the study visit; the Investigator will review and approve the completed CRFs.

The information collected on CRFs shall be identical to that appearing in original source documents. Source documents will be found in the patient's medical records maintained by UCSF personnel. All source documentation should be kept in separate research folders for each patient.

In accordance with federal regulations, the Investigator is responsible for the accuracy and authenticity of all clinical and laboratory data entered onto CRFs. The PI will approve all completed CRFs to attest that the information contained on the CRFs is true and accurate.

All source documentation and CTMS data will be available for review/monitoring by the UCSF DSMC and regulatory agencies.

The Principal Investigator will be responsible for ensuring the accurate capture of study data. At study completion, when the CRFs have been declared to be complete and accurate, the database will be locked. Any changes to the data entered into the CRFs after that time can only be made by joint written agreement among the Study Chair, the Trial Statistician, and the Protocol Project Manager.

